13.1.2 Evaluability for preliminary evidence of response

All eligible patients who received at least one dose of the study drug will be evaluable for response assessment.

13.2 Study Design/Endpoints

This is a phase I study and we will use the Rolling-6 design for dose finding.

Since myelosuppression is the predominant side effect of this agent, the phase I study will first evaluate the toxicities in children who have not been heavily pre-treated previously. Once MTD has been established in this cohort of patients, consideration will be given to expanding the trial to include those who have received intensive cytotoxic therapy including myeloablative chemotherapy +/- craniospinal irradiation.

As of version 4 and following the declaration of MTD in Stratum I, we will initiate enrollment in Stratum II for heavily pre-treated patients. The initial treatment dose for these patients will be one dose level below the MTD in stratum I and escalation to the MTD of stratum I will be pursued, if the initial dose level is well tolerated.

Rolling-6 Design

A "Rolling-6" Phase I design will be used to estimate the maximum tolerated dose (MTD), where dose escalations are planned in cohorts of two-six patients. No intra-patient escalation will

be allowed. The same algorithm will be used in both strata I and II but will proceed independently. The maximum dose to be studied in Stratum II will be the MTD for Stratum I.

Skolnik et al recently introduced the Rolling-6 design,³¹ motivated by the observation that most pediatric Phase I trials in oncology have not produced excessive toxicities. A possible explanation for this could be that pediatric studies are often preceded by adult trials and the knowledge gained in the latter is utilized towards ensuring safety in the former. The Rolling-6 design aims to shorten the duration of pediatric Phase I trials by minimizing the time the trial would be closed to accrual for toxicity monitoring. This is achieved by enrolling anywhere from 2 to 6 patients at a dose level without requiring that the DLT status of the patients already assigned to the same dose level are known, reducing the number of patients who would be turned away due to unavailability of open slots. The simulations in Skolnik et al. as well as PBTC's own simulations indicate that this approach decreases the duration of a Phase I trial compared to the traditional method without increasing the overall incidence of toxicity.

Dose Escalation/De-Escalation Rules

The Rolling-6 design allows for accrual of two to six patients concurrently onto a dose level. Decisions as to which dose level to enroll a patient are based on the number of patients currently enrolled and evaluable, the number of patients experiencing dose-limiting toxicities (DLT), and the number of patients still at risk of developing a DLT at the time of new patient entry. Dose escalation occurs if 0 of 3-6 or no more than 1 of 6 evaluable patients experience a DLT while being treated at a dose level; otherwise if 2 of 2-6 patients experience DLTs the dose is declared too toxic and thus above the MTD. Once a dose is determined to be too toxic, further dose escalation is not allowed. The MTD is empirically defined as the highest dose level at which six patients have been treated with at most one patient experiencing a DLT and the next higher dose level has been determined to be too toxic.

The following table enumerates all possible scenarios and describes escalation/de-escalation rules for a rolling 6 design.

Dose Escalation/De-Escalation Rules for the Rolling-6 Design					
# Pts. Enrolled	# Pts. with DLTs	# Pts. w/o DLT	# Pts. with Toxicity Data Pending	Decision when Next Patient is Enrolled	
				Not at the Highest Dose Level	At the Highest Dose Level
2	0, 1	Any	Any	Stay	Stay
2	2	0	0	De-escalate	De-escalate
3	0	0, 1, 2	3, 2, 1	Stay	Stay
3	0	3	0	Escalate	Stay
3	1	0, 1, 2	2, 1, 0	Stay	Stay
3	≥ 2	Any	Any	De-escalate	De-escalate
4	0	0, 1, 2, 3	4, 3, 2, 1	Stay	Stay

4	0	4	0	Escalate	Stay
4	1	0, 1, 2, 3	3, 2, 1, 0	Stay	Stay
4	≥ 2	Any	Any	De-escalate	De-escalate
5	0	0, 1, 2, 3, 4	5, 4, 3, 2, 1	Stay	Stay
5	0	5	0	Escalate	Stay
5	1	0, 1, 2, 3, 4	4, 3, 2, 1, 0	Stay	Stay
5	≥ 2	Any	Any	De-escalate	De-escalate
6	0	0, 1, 2, 3, 4	6, 5, 4, 3, 2	Suspend	Suspend
6	0	5, 6	1, 0	Escalate	MTD not determined
6	1	0, 1, 2, 3, 4	5, 4, 3, 2, 1	Suspend	Suspend
6	1	5	0	Escalate	MTD not determined
6	≥ 2	Any	Any	De-escalate	De-escalate

Based on the above-outlined escalation rules, if dose level 1 is found to be too toxic in either stratum, then accrual to that stratum will be suspended and the merits of amending or closing the stratum permanently will be reconsidered. On the other hand, if the maximum dose level proposed for the study is deemed to be safe, then the MTD will not have been determined and consideration may be given to investigate higher dose levels. Alternatively, the highest dose level may be recommended as the Phase II dose.

Once the MTD has been estimated or the recommended Phase II dose has been determined, 6 additional patients will be treated at that dose level to better describe the toxicity profile of the agent. If the number of toxicities observed in the expansion cohort suggests that the initial estimate of the MTD is too toxic then we will consider de-escalating to a lower dose level and treating additional patients at that level including an expansion cohort in an effort to estimate the phase II recommended dose.

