2.2.3 Adult Clinical Trials

2.2.3.1 Phase I trial of PD-0332991 in adults with recurrent solid tumors
PD-0332991 has been tested in a Phase I trial in adults with recurrent solid tumors and lymphomas (A5481001) that explored two different schedules of the drug. In the first schedule reported by Schwartz et al., adult patients with Rb1 positive recurrent solid tumors were enrolled

across four cohorts using doses of 100 mg, 150 mg, 200, and 225 mg given orally daily for 14 days every 3 weeks (Schedule 2/1).³ No DLTs were observed at the 100 mg or 150 mg dose level. Dose limiting myelosuppression occurred in 2/3 patients at the 225 mg dose level [Grade IV neutropenia and thrombocytopenia (n=1) and Grade III neutropenia with delayed recovery (n=1)]. An intermediate dose of 200 mg/day was chosen. After only one DLT was observed (Grade III neutropenia and thrombocytopenia) in 6 enrolled patients at this dose, the cohort was expanded to a total of 20 patients. Three additional patients suffered DLT (Grade III myelosuppression with delayed recovery) with an overall 20% rate of DLT at this dose level. Since this did not exceed the preset limit of 33%, 200 mg/day for 14 days every 4 weeks was declared the MTD. Additional toxicities were mild and included Grade I fatigue and Grade I-II diarrhea. No patient had Grade 3 prolongation of QTc interval on EKG during therapy. Plasma PK studies revealed a dose proportional increase in C_{max} and AUC_{0-10} on days 1 and 8. In samples obtained from patients receiving 200 mg q daily, repeated dosing led to steady state levels. The median T_{max} was 4.2 hours and volume of distribution was 3241 liters (more than the adult total body water of 42 liters) suggesting extensive tissue penetration. PD-0332991 was eliminated slowly with a mean $T_{1/2}$ of 26.7 hours.²¹ One patient with a non-seminomatous germ cell tumor of the testis achieved a prolonged partial response and 9 had SD. Six patients with SD had treatment for ≥ 4 cycles and 2 for ≥ 10 cycles.

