5.1.2 Dose Escalation Schedule

The pediatric equivalent of the adult MTD for the once daily administration of PD-0332991 (IBRANCE) based on a 3-week on/1 week off schedule is approximately 75mg/m². PD-0332991 (IBRANCE) dosing will begin at 50 mg/m². The PD-0332991 (IBRANCE) dose will be increased in subsequent cohorts until the MTD is reached ([Table 7](#)) or the highest proposed dose is determined to be safe.

The

[Table 7](#) below lists the proposed dose levels to be studied along with the BSA restrictions for each dose level for both Strata I and II. At the time of submission of version 8.0, a total of 21 patients had been enrolled in stratum I. No DLTs were observed in 3 patients enrolled in dose

level 1 and 6 patients enrolled in dose level 2. At dose level 3, a total of 6 patients were enrolled and 2 were inevaluable for toxicity assessment. Two of 4 evaluable patients at this dose level experienced DLTs (grade 4 neutropenia); hence the MTD was exceeded at dose level 3. The MTD for stratum I was determined as dose level 2 (75 mg/m²/day) and this stratum has been closed to accrual.

The starting dose level for stratum II is one dose level below the stratum I MTD (i.e. 50 mg/m²/day). If this dose is well tolerated in the initial cohort of patients enrolled on Stratum II, the dose will be escalated to 75 mg/m²/day for the next cohort of patients. No further escalation will be allowed in this stratum.

[figure not shown]
The plot below the table demonstrates that dosing using the available capsule sizes is feasible for the proposed dose levels using the BSA restrictions outlined in the table below. It is not however possible to include a level below 50mg/m²/day due to the capsule size limitations. No intra-patient dose escalation will be permitted on the protocol. Only DLTs observed during the dose-finding period will be used to guide dose escalation. Dose escalation will be governed by the Rolling-6 statistical design separately in each of the two strata, as described in section [13.2](#) of the protocol.

Table 7
Stratum I and II: PD-0332991 (IBRANCE) Dosing Regimen and BSA Restrictions

Dose Level	Dose (mg/m ²)	BSA (m ²)
1*	50	≥ 1.20
2**	75	≥ 0.93
3	95	≥ 0.70

* Starting dose for Stratum II

** MTD for stratum I

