6.2 Hematologic and Non-Hematologic Adverse Events and Management

Table 8

Event	AE Grade or Observation	Dose Modification
Diarrhea or other non-hematologic toxicity	Grade 1 or 2	Maintain dose; continue anti-diarrheal treatment.
	Grade 3 (non-dose limiting)	Hold PD-0332991 (IBRANCE) and maximally treat. If toxicity resolves to meet on study parameters within 14 days of drug discontinuation or (as outlined in Section 5.2.1.1), restart treatment at the same dose.
	Grade 3 or 4 (dose limiting)	Hold PD-0332991 (IBRANCE) and maximally treat. If toxicity resolves to meet on study parameters with 14 days of drug discontinuation, restart treatment at next lower dose level if patient at dose level 2 or 3 and meets BSA requirements for the next lower dose level. If patient at dose level 1 or with BSAs smaller than what is required should come off treatment permanently. If toxicity does not resolve to meet study eligibility parameters within 14 days of drug discontinuation, the patient must be removed from protocol therapy. If dose limiting toxicity recurs in a patient who has resumed treatment at the reduced dose level, the patient must be removed from protocol therapy.
Hematologic	Grade 1 or 2	Maintain dose.
	Grade 3 (non-dose limiting)	Maintain dose.
	Grade 3 or 4 (dose limiting)	Hold PD-0332991 (IBRANCE). Counts should be checked at least twice weekly (3-4 days apart) during this time. If toxicity resolves to meet on study parameters with 14 days of drug discontinuation, restart treatment at next lower dose level, if patient is at dose level 2 or 3 and meets BSA requirements for the next lower dose level. If patient at dose level 1 or with BSAs smaller than what is required should come off treatment permanently. If toxicity does not resolve to meet study eligibility parameters within 14 days of drug discontinuation, the patient must be removed from protocol therapy. If dose limiting toxicity recurs in a patient who has resumed treatment at the reduced dose level, the patient must be removed from protocol therapy.

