13.3 Sample Size/Accrual Rate

Projected Accrual Rates and Study Duration

Though it is difficult to come up with a precise estimate for recurrent pediatric brain tumor patients, we are estimating that up to 30% of patients screened will be Rb1 negative as measured by IHC and thus will not be eligible for this trial. The maximum sample size for stratum I is 24 eligible and evaluable patients if all 3 dose levels are studied and taking into account the expansion cohort at the MTD (barring excessive toxicities at the expansion cohort). Hence we may need to screen up to 35 patients in order to enroll 24 eligible patients in stratum I.

Based on the available information as of version 4.0, dose level 3 will not be studied in Stratum II and thus with two possible dose levels to be studied, the maximum number of patients to be enrolled on Stratum II is 18 (barring excessive toxicities at the expansion cohort). Though less information is available about the potential patient cohort for stratum II, if we assume that 30% of patients screened will be Rb1 negative as measured by IHC, then we may have to screen 25 patients in order to be able to enroll 18 eligible and evaluable patients.

As of version 8.0, 25 patients had been enrolled on this study; 21 in stratum I and 4 in stratum II.

For stratum I, the MTD has been determined as dose level 2 (75 mg/m²/day) and this stratum has been closed to accrual. Accrual for stratum II was recently initiated at 50 mg/m²/day, which is one dose level below the stratum I MTD. Four patients have been enrolled at this dose level to date. The intent is to either determine a new MTD for this stratum which is lower than 75 mg/m²/day or establish that the stratum I MTD is also safe in this patient cohort. The accrual to the trial is ongoing.

Considering that there are always patients who enroll on Phase I trials but are not evaluable for dose finding we may need to screen as many as 55 patients in total for both strata.

The accrual rate for most of our Phase I trials open to all recurrent patients is typically 2-3 patients/month. Considering that eligibility to this study will be limited to patients with available tissue for IHC analysis and among those only to patients with Rb1 + tumors, accrual rate is estimated to be 1-2 eligible patients per month per stratum. Hence we expect to complete accrual to each stratum within 1-2 years of initiating enrollment.

Accrual Targets				
Ethnic Category	Sex/Gender			
	Females		Males	Total

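### If dose level 1 becomes the stratum II MTD and its expansion proves toxic, does section 13.2 leave the team without a workable rule?

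*Combined protocol and SAP*

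**What the plan says.** **Escalation rule (13.2).** Up to six patients are treated per level. A level passes with at most one DLT in six; "otherwise if 2 of 2-6 patients experience DLTs the dose is declared too toxic and thus above the MTD".

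**Level 1 provision (13.2, after the Rolling-6 table).** The sentence opens "Based on the above-outlined escalation rules, if dose level 1 is found to be too toxic in either stratum" and goes on to suspend accrual to that stratum while amendment or permanent closure is weighed.

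**Expansion (13.2, next paragraph).** Six more patients are treated at the MTD or recommended Phase II dose to describe the toxicity profile better. The trigger reads "If the number of toxicities observed in the expansion cohort suggests that the initial estimate of the MTD is too toxic", and the response is "then we will consider de-escalating to a lower dose level and treating additional patients at that level including an expansion cohort".

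**Lowest level (5.1.2).** "It is not however possible to include a level below 50mg/m²/day due to the capsule size limitations".

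**Stratum II (13.3).** Two levels are open, and level 1 is the starting level. "The intent is to either determine a new MTD for this stratum which is lower than 75 mg/m²/day"; the alternative is to show that the stratum I MTD is safe here too. The maximum of 18 patients is stated on condition that the expansion shows no excessive toxicity. At protocol version 8.0, four patients had been enrolled, all at level 1.

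**The concern.** An MTD below 75 mg/m²/day in stratum II can only be level 1, and the Schema expects more myelosuppression in this stratum, so a level 1 expansion is foreseeable. If it proved too toxic, the expansion clause would point to a level that does not exist. The suspension sentence would fit, but it is tied to the escalation rules, whose table stops at six patients, and nothing says that it reaches the expansion. Section 6.2 does deal with the lack of a lower level for an individual patient ("If patient at dose level 1 or with BSAs smaller than what is required should come off treatment permanently"); the expansion clause is silent on it.

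The trigger also has no number. The adult trial summarised in 2.2.3.1 judged its expanded cohort on the pooled count, 4/20 = 20%, against a limit of 33% set beforehand. Here the count and the denominator (six or twelve) would be chosen after the data are seen. The MTD in each stratum is primary objective 1.1.1, so the worry is that its value could turn on a late choice of rule.

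**Working it through.** **1. The plan's own figures.** Maximum sample size = levels × 6 + 6.
- Stratum I: 3 × 6 + 6 = 24, as stated.
- Stratum II: 2 × 6 + 6 = 18, as stated.
- Stratum II with the expansion at level 1: 6 (level 1) + 6 (level 2) + 6 (expansion) = 18.
- Stratum II with a level 2 expansion that fails: 12 at level 2 + 6 + 6 at level 1 = 24. Section 13.3 leaves room for this by making 18 conditional.

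**2. Which step is available after a toxic expansion.**
- At level 2, level 1 lies below it, so the expansion clause can be carried out.
- At level 1, no lower level exists, so considering one ends there. The level 1 provision in the same section, worded for either stratum, is what remains.
- The expansion clause applies when the MTD estimate is judged too toxic; the level 1 provision applies when level 1 is found too toxic. Once either condition is met, level 1 is not confirmed. No reading of the two sentences both declares level 1 too toxic and keeps it as the MTD.

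**3. How often the disputed case arises.** Three things must all happen: level 1 passes (at most 1/6), level 2 fails (at least 2/6), and the level 1 expansion is called too toxic. For the last, take at least 2/6 in the expansion alone. The documents give no true DLT rates, so the rates p1 (level 1) and p2 (level 2) are assumptions, with independent binomial counts.

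P(X ≥ 2 of 6) = 1 − (1−p)^6 − 6p(1−p)^5, which gives 0.1143 (10%), 0.2632 (1/6), 0.3446 (20%), 0.6488 (1/3) and 0.7667 (40%).

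| p1 / p2 | level 1 passes × level 2 fails × expansion ≥ 2/6 | Joint |
|---|---|---|
| 10% / 10% | 0.8857 × 0.1143 × 0.1143 | 1.2% |
| 10% / 20% | 0.8857 × 0.3446 × 0.1143 | 3.5% |
| 1/6 / 20% | 0.7368 × 0.3446 × 0.2632 | 6.7% |
| 1/6 / 1/3 | 0.7368 × 0.6488 × 0.2632 | 12.6% |
| 20% / 1/3 | 0.6554 × 0.6488 × 0.3446 | 14.7% |
| 20% / 40% | 0.6554 × 0.7667 × 0.3446 | 17.3% |

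The separate probabilities, up to 76.7% for a failed level 2 and 64.9% for two or more DLTs in an expansion, overstate the exposure because the events must coincide.

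A pooled trigger makes the case rarer. Given at most 1/6 first, the chance of at least 3/12 is 0.0552 at 10% and 0.2463 at 20%; of at least 4/12, 0.0071 and 0.0661. The last row becomes 0.6554 × 0.7667 × 0.2463 = 12.4% or × 0.0661 = 3.3%. The first becomes 0.8857 × 0.1143 × 0.0552 = 0.6% or × 0.0071 = 0.1%.

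**4. What two DLTs in the expansion would mean.** After 0/6 the level total is 2/12 = 1/6, the proportion 13.2 accepts. After 1/6 it is 3/12, between the accepted 1/6 and the rejected 2/6 (= 4/12). So 2/6 in the expansion does not by itself condemn the level on the plan's own proportions.

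**5. Would a pooled limit settle it?** 2/12 and 4/12 match proportions already in 13.2; only 3/12 is open. Its exact 95% interval is 5.5% to 57.2%, and that for 4/12 is 9.9% to 65.1%. The two overlap almost entirely, so twelve patients give little statistical ground for where to cut.

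**The case for a change.** The strongest case for a change is that the limit matters and is cheap to fix now. Given at most 1/6 in the first six, a dose with a true DLT rate of 1/3 would be overturned 26.5% of the time with a 4/12 limit and 56.7% with 3/12; at 40%, the figures are 40.0% and 70.5%. With four stratum II patients enrolled at version 8.0, a limit could be fixed before any expansion data exist, at no cost in patients.

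These figures stand, and so does the observation that 13.2 states no count. It is also true that applying the suspension sentence to an expansion is an inference.

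They do not show that a stated rule gives a wrong result. The plan describes the expansion as a fuller look at toxicity and leaves the decision to judgement. It refers to toxicities in the expansion cohort, so pooling over twelve and counting only DLTs would be a new design choice. The adult trial's 33% limit is background and binds nothing here. A fixed cut also has a price: moving the limit from 4/12 to 3/12 raises the chance of overturning a 20% dose from 6.6% to 24.6%. Reading 2/6 in the expansion alone departs from a pooled 3/12 limit only at 0/6 then 2/6, which has a chance of 5.9% to 9.8% over true rates from 10% to 40%. What counts as a DLT is already fixed in 5.2.1, and 13.4 reports adverse events for each stratum by dose, attribution and grade, so readers can see the basis for whatever the team decides.

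**Conclusion.** No change to the plan follows. The expansion clause and the level 1 provision do not contradict each other; a cross-reference between neighbouring paragraphs is missing. A team facing a toxic level 1 expansion would find no lower level to consider and would turn to the provision for a too-toxic level 1 in the same section. Neither route confirms level 1 as the MTD.

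The unstated trigger is a gap in detail in a review that the plan leaves to judgement, and a pooled limit is a debatable preference with little gain at twelve patients. The disputed case has a chance of about 1% to 17% with 2/6 in the expansion as the trigger, and less with a pooled one. Those figures rest on assumed DLT rates (10% to 20% at level 1, 10% to 40% at level 2) and independent patients. The stratum I MTD and the maxima of 24 and 18 are not called into question. No limit, dose or consequence is recommended here.

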13.3 Sample Size/Accrual Rate

Projected Accrual Rates and Study Duration

Though it is difficult to come up with a precise estimate for recurrent pediatric brain tumor patients, we are estimating that up to 30% of patients screened will be Rb1 negative as measured by IHC and thus will not be eligible for this trial. The maximum sample size for stratum I is 24 eligible and evaluable patients if all 3 dose levels are studied and taking into account the expansion cohort at the MTD (barring excessive toxicities at the expansion cohort). Hence we may need to screen up to 35 patients in order to enroll 24 eligible patients in stratum I.

Based on the available information as of version 4.0, dose level 3 will not be studied in Stratum II and thus with two possible dose levels to be studied, the maximum number of patients to be enrolled on Stratum II is 18 (barring excessive toxicities at the expansion cohort). Though less information is available about the potential patient cohort for stratum II, if we assume that 30% of patients screened will be Rb1 negative as measured by IHC, then we may have to screen 25 patients in order to be able to enroll 18 eligible and evaluable patients.

As of version 8.0, 25 patients had been enrolled on this study; 21 in stratum I and 4 in stratum II.

For stratum I, the MTD has been determined as dose level 2 (75 mg/m²/day) and this stratum has been closed to accrual. Accrual for stratum II was recently initiated at 50 mg/m²/day, which is one dose level below the stratum I MTD. Four patients have been enrolled at this dose level to date. The intent is to either determine a new MTD for this stratum which is lower than 75 mg/m²/day or establish that the stratum I MTD is also safe in this patient cohort. The accrual to the trial is ongoing.

Considering that there are always patients who enroll on Phase I trials but are not evaluable for dose finding we may need to screen as many as 55 patients in total for both strata.

The accrual rate for most of our Phase I trials open to all recurrent patients is typically 2-3 patients/month. Considering that eligibility to this study will be limited to patients with available tissue for IHC analysis and among those only to patients with Rb1 + tumors, accrual rate is estimated to be 1-2 eligible patients per month per stratum. Hence we expect to complete accrual to each stratum within 1-2 years of initiating enrollment.

Accrual Targets				
Ethnic Category	Sex/Gender			
	Females		Males	Total
Hispanic or Latino	5	+	6	= 11
Not Hispanic or Latino	22	+	22	= 44
Ethnic Category: Total of all subjects	27	+	28	= 55
Racial Category				
American Indian or Alaskan Native	0	+	0	= 0
Asian	3	+	3	= 6
Black or African American	6	+	7	= 13
Native Hawaiian or other Pacific Islander	0	+	0	= 0
White	18	+	18	= 36
Racial Category: Total of all subjects	27	+	28	= 55

13.4 Analysis of the Adverse Event Data:

All patients who receive at least 1 dose of protocol therapy will be included in the safety analyses. Adverse event data will be summarized in stratum specific tables which will incorporate dose, attribution as well as grade information.

13.5 Data analysis plan for the secondary objectives:

Any objective responses (PR+CR) which may be observed in this trial will be described by dose and by histology. We will also report prolonged disease stabilizations in a descriptive fashion.

The biology and PD/PG studies are optional in this trial and thus data will be available only from a subset of patients who are likely to represent a variety of histologies. The data generated as part of these correlative studies will be described and summarized in an exploratory fashion via summary statistics and frequency tables as appropriate.

